12.3 Planned Interim Analyses (if applicable)

No interim analyses are planned unless the DSMB recommends interim analyses.

12.4 Final Analysis Plan

Intent-to-treat (ITT) analyses standard in incentive based behavioral economics studies will be utilized (e.g. Halpern *et al.* 2015, Patel *et al.* 2016). Generalized linear mixed models (GLMMs) will be used to compare primary and secondary outcomes over time between groups. GLMMs make fewer missing data assumptions than other methods, which assume missing data are missing completely at random. Identity link will be used for numeric (interval) outcomes (e.g., mean number of qualifying half-day toothbrushing episodes per week, through Month 6 visit; mean OHI-MIS plaque score; and TP pump weight change). The group x time interaction will also be assessed; short-term effects will be assessed for 1 month of the intervention, mid-term effects after the novelty effect of powered toothbrushing usually ends for the Month 3 Visit, and long-term effects for the Month 6 Visit (primary outcome), as well as, maintenance of behavior after removing the incentives for the Month 12 Visit. Recent, powerful Precision Medicine methods which do not inflate Type I error will be used to detect heterogeneity of treatment effects by groups of participants based on baseline characteristics (e.g., Lazar *et al.* 2013). Multiple imputation using chained equations (MICE) for arbitrary missingness patterns (Raghunathan *et al.* 2001; van Buuren 2007) will be used for sensitivity analyses. Supplemental analyses will also explore: a) trajectories of mean number of qualifying half-day brushing episodes per week over time; as well as b1) variability in morning brushing times, b2) variability in evening brushing times, and c) variability in weekday versus weekend brushing times associated with mean number of qualifying half-day brushing episodes, OHI-MIS plaque scores, and ASTDD BSS caries screening measures.

To examine potential impact of timing of drawing reward communication time, GLMM analyses as above will be performed comparing the weekly and quarterly drawing result communication arms for primary and secondary outcome data from Month 12 to Month 18.

To investigate the behavioral economics mechanisms through which behavior change outcomes may have operated, **mediation analyses** will be conducted with the measures of risk preferences (i.e., for the presence of prospect theory tendencies), time preferences (i.e., for the presence of present bias), and forgetfulness (i.e., for attention). Each of these factors will be investigated in separate models to assess the extent the particular underlying construct lies within the pathway toward toothbrushing behavior change (i.e., by reducing the estimate of the ITT main effect).

In addition, because parents and children with different backgrounds (e.g., child's age, parent's/caregiver's education) and behavioral, normative, and control beliefs may respond differently to the incentives given, heterogeneity of treatment effect analyses will be conducted to identify groups influenced by the intervention. For example, the UH2 pilot (White *et al.* 2020) suggested the intervention on toothbrushing frequency may vary by child age (<24mo vs \geq 24mo). The results of these analyses will also inform the sampling frame for the parent FGDs so that important dimensions of diversity can be represented.

We will assess **cost-effectiveness** and **return on investment** in three steps. First, we will assess the net cost of the intervention and its consequences, using micro-costing and modeling techniques. Costs for the intervention itself will include mainly personnel to implement the intervention (in particular, training on toothbrush software use), the cost of the toothbrush, the value of the financial incentives, and incentive administration. This will be assessed through a combination of financial record review (e.g., expenditures and human resources) and observation of project activities via staff activity logs. We will also cost the change in health care utilization precipitated by the intervention: both increased preventive care and decreased restorative care. This will be assessed combining utilization with standard values for unit cost, based on payment rates by Medi-Cal and other payers. Together, these generate net costs. We will also estimate toothbrushing time (including preparation) by caregivers. Second, we will quantify the health benefits of the intervention, including dental health events (e.g., number of carious lesions) and quality-adjusted life years (QALYs) which translate morbidity in the short term (measured in Aim 4) and long term (projected based on published longitudinal clinical studies) into a standard metric of health status. Health state utility data (for QALYs) will derive from studies in the literature. The analysis of expected costs and QALYs in the intermediate and long-term will be structured using a spreadsheet-based decision-analysis created for this purpose in consultation with clinical experts. Third, we will calculate the economic outcome measures including **incremental cost-effectiveness ratio (ICER)** and **return on investment (ROI)**. The ICER is the ratio of net cost to health gain, comparing the intervention and control arms. It is indicated if the intervention has a net cost (i.e., does not save money) while improving health outcomes (QALYs gained). The ROI calculates annual rate of return over a specified time period (e.g., 30 years), by comparing expenditures and savings in each year. It is indicated if the intervention generates net savings, i.e., reductions in dental care costs exceed implementation costs. We will also calculate ROI using

willingness-to-pay for a QALY gained. All analyses will be repeated for 1, 2, 5, 10, & 20 years, and subjected to extensive sensitivity analyses to test the impact of uncertainty on results.

The FGD and stakeholder interview audio recordings will be transcribed. One research assistant will transcribe the English interviews and third party translating services, Language Service Solutions (LSS), will translate and transcribe Spanish interviews into English. One fluent Spanish and English reading, writing, and speaking research assistant will review all LSS English translated transcriptions for cultural language accuracy. Two independent coders will use general thematic analysis to code excerpts (i.e., parent codes and child sub-codes will be derived from data rather than *a priori*) from interview transcripts using web-based Dedoose qualitative software. To develop the final codebook, each coder will iteratively review several transcripts to develop an initial list of codes, which will then be merged and reconciled to refine code definitions and hierarchies, a process that will be repeated until only minor adjustments to the codebook result. Using the agreed-upon codebook, each coder will then individually code each transcript and results will be compared and discussed to calibrate intercoder reliability. Preliminary themes relating to factors explaining the intervention impact and perspectives on behavior change motivation, as well as overall program acceptability will be analyzed and discussed to reach theme consensus.

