4 STUDY DESIGN

We will conduct a stratified RCT testing the impact of monetary rewards on ECC preventive behaviors and oral health. Eligible child-parent/caregiver participant dyads will be consented, enrolled, and, following a 2 week run-in, randomized within strata and permuted blocks in equal allocation to one of two groups: 1) Monetary Rewards or 2) Delayed Reward Control. Strata will be based on site and smartphone operating system. The intervention will be offered for 6 months, and children (ages 6 months through <48 months) will be followed for 12 months to determine reward effects on dental visit attendance, toothbrushing, fluoride TP use, OHI-MIS plaque score , and caries screening status. Results will inform researchers and public health practitioners on the longer-term maintenance of behavioral changes and oral health screening status following removal of the rewards.

The study population will be predominantly low income Hispanics/Latinos who are parents/caregivers with children enrolled in, or waitlisted for, one of the participating Los Angeles County EHS or affiliated day care center programs. After enrollment parents/caregivers will use powered toothbrushes for a 2 week run-in to ensure their technology works and they are willing to follow study procedures; after the enrollment visit and run-in, randomization will occur at a separate visit. Participants who are unable to provide data during the run-in period will not be randomized or continue in the study.

Participants in the Monetary Reward group will be eligible to earn one of two incentive amounts every week for the first 6 months of the trial. A participant who meets a low or high threshold will earn entry in that week's drawing for financial incentives (See Section 6.1 for additional details).

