5.4 Treatment Assignment Procedures

A randomization schedule will be generated by the Coordinating Center (CC) and stored in REDCap to randomize consenting parent/caregiver-child dyads into one of two groups. Once eligibility is confirmed, informed consent is documented, the run-in period is completed, and a staff member confirms the app has been properly installed and maintained, the project manager will click the "randomize" button in REDCap to reveal group assignment for the parent/caregiver-child dyad.

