5.4.1 Randomization Procedures

A custom SAS program using PROC PLAN stratifying on site (facility type) and phone type (iPhone or Android) as well as permuted blocks of varying sizes will be utilized with a random seed based on the date the program is first modified from the program used in the pilot trial. The randomization schedule will be stored on the secure UCSF CC server in a restricted permissions folder, as well as, in REDCap. Only staff needing to administer the intervention, or the DSMB if needed for safety reasons, will be unblinded before completion of the trial. Randomized arm assignment will not be unblinded to

other team members until the trial is completed or has been stopped early by NIDCR or the DSMB.

5.4.2 *Masking Procedures*

An independent dental examiner and PIs will be blinded to participants' group assignment, and participants will be told that the examiner and PIs cannot answer any incentive questions and they should not mention the incentive program to them. Due to the nature of the intervention, the staff explaining the study arms after randomization and providing the incentive gift cards at Month 3, 6, 9, 12, 15, and 18 visits cannot be blinded. At the Month 6 and 12 visits, dental screenings will precede monetary incentive payment.

5.5 *Subject Withdrawal*

Participants may withdraw voluntarily from the study at any time.

5.5.1 *Reasons for Withdrawal*

Participants may decide not to answer any Computer Assisted Personal Interview (CAPI) item or not to participate in the study at any time without penalty.

Participants are free to withdraw from participation in the study at any time upon request, for any reason, without penalty or loss of benefits as a member of their EHS or affiliated day care program or health clinic. This may occur due to discomfort with questions or practical concerns that limit the time available (e.g., pressing employment schedule or child care needs).

An investigator may terminate a study participant's participation in the study if:

- Any clinical adverse event (AE) or other medical condition or situation occurs such that continued participation in the study would not be in his/her best interest.
- The participant meets an exclusion criterion (either newly developed or not previously recognized) that precludes further study participation.
- Participants who are unable to provide app data during the run-in period will be withdrawn prior to randomization.

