6.2 Administration of Intervention

All participants will be instructed to sync their smart powered toothbrushing data to the app three times per week. Failure to sync three times per week will disqualify the participant from receiving any incentives that week for those in an incentive group. All participants, regardless of group assignment, will receive a fixed payment of \$1 per sync for syncing their data up to three times per week (Wednesdays, Fridays, and Sundays, specifically). A text message reminder to sync the app will be sent to participants before each of these three times every week.

First, all participants will enter two initial “practice” (run-in) weeks at the start of the intervention, during which participants will sync their toothbrushing data (and be eligible for up to \$3 of incentives for syncing), but will not be eligible for the performance-based toothbrushing reward. Following the two practice weeks, intervention group participants are eligible to earn rewards over the first 24 weeks (6 months), while Delayed Monetary Reward Control group participants may earn rewards between the 12-month visit and 18-month visit.

All participants will be sent text messages of their toothbrushing performance status each week, per the powered toothbrushing data. For participants assigned to the intervention group, the text message will include the amount earned and the total gift card balance accrued to date for the previous 3-month period. Additionally, participants will have the option to have text messages sent to other family members who regularly brush the child’s teeth and who consent by text message to receiving messages. Contact information for all family members will be obtained at the baseline visit.

Thus, the total expected payout value of attaining the high toothbrushing adherence threshold throughout the 6-month intervention period is \$240.

To claim any incentives, including for syncing data, a parent/caregiver and child must attend the follow-up visits. Based on developmental stage telephone survey preferences, all earned reward payments will be awarded as gift cards at the Month 3 and Month 6 visits for the Monetary Reward group, and Month 15 and Month 18 visits for the Delayed Monetary Reward Control group. Syncing payments will be awarded as gift cards at all follow-up appointments.

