7.1.2 Baseline (Post-Run-In/Randomization) Visit (Visit 2, $T = 0$ [+10/-2])

- Administer CAPI questionnaire to parent/caregiver.
- Click the REDCap “randomize” button to reveal participant’s randomized assignment to arm. Explain the intervention procedures and rewards program (if assigned to the Intervention Arm) to the parent/caregiver and have her/him explain it back in her/his own words. Explain control procedures (if assigned to the Control Arm) to the parent/caregiver and have her/him explain it back in her/his own words.
- Schedule the family’s next visit (in approximately 3 months) and give the parent/caregiver \$30 compensation for attending the baseline visit.

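### The primary model names neither run-in brushing nor the randomisation strata as covariates, so precision the trial already has may go unused

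*Combined protocol and SAP*

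**What the plan says.** Section 12.4 gives the model in two statements: "Generalized linear mixed models (GLMMs) will be used to compare primary and secondary outcomes over time between groups", and "The group x time interaction will also be assessed". The link is the identity for numeric outcomes. No covariate or stratum is named for the primary comparison. Baseline characteristics come up only under heterogeneity of treatment effect.

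Elsewhere the document describes data that could serve as covariates:

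- **Run-in brushing.** Section 4 says "After enrollment parents/caregivers will use powered toothbrushes for a 2 week run-in", with randomisation at a separate, later visit, and "Participants who are unable to provide data during the run-in period will not be randomized or continue in the study". Section 5.4 allows randomisation only once "the run-in period is completed, and a staff member confirms the app has been properly installed and maintained". Section 7.1.2 is headed "Baseline (Post-Run-In/Randomization) Visit".
- **Strata.** Section 5.4.1 describes an allocation schedule "stratifying on site (facility type) and phone type (iPhone or Android".

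Section 6.2 reads differently on timing. It calls the practice weeks "weeks at the start of the intervention, during which participants will sync their toothbrushing data".

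**The concern.** Run-in brushing is the primary outcome itself, recorded before allocation with the same brush and app and with no performance reward on offer. Some of it should exist for every randomised dyad, although no minimum number of synced days is set. Brushing varies widely between families: Section 12.2 reports a pilot SD of 4.8 on a mean of 5.5 episodes per week. Whatever part of that variation is stable within a family stays in the error term if the run-in value is left out, and the interval for the reward effect is wider than it need be.

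Leaving out the strata has a smaller effect of the same kind. Stratified allocation balances the arms on site and phone type, but an analysis that ignores them reports a standard error that is slightly too large.

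The timing conflict adds a separate risk. The primary outcome runs through the Month 6 visit with no stated first week. A reader of Section 6.2 alone could count the practice weeks in it, and those unrewarded weeks would dilute the group difference.

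Section 12.4 is also silent on how the screening plaque score enters the plaque model.

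**Working it through.** **Inputs from Section 12.2:** 91 per group, difference 2.65, SD 6.0 (pilot SD 4.8 × 1.25), two-sided alpha 0.05, 244 dyads at 75% retention.

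**Assumed inputs, not in the documents:** r = 0.1 to 0.7, and the share of outcome variance explained by the strata, 2% to 10%.

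**1. The plan's own figure.** Standard error = 6.0 × √(2/91) = 0.889. Noncentrality = 2.65/0.889 = 2.98 on 180 degrees of freedom. Noncentral t power = 84.2%, against 84% stated. For enrolment, 91/0.75 = 121.3, rounded up to 122 per group, gives 244. Both figures reproduce.

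**2. Adjusting for run-in brushing.** Residual SD = SD × √(1 − r²), with the same power formula. Interval half-width = 1.973 × residual SD × √(2/91).

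| r | Residual SD (SD 6.0) | Power, SD 6.0 | Half-width, SD 6.0 | Narrowing | Power, SD 4.8 |
|---|---|---|---|---|---|
| 0 | 6.00 | 84.2% | 1.755 | – | 95.9% |
| 0.1 | 5.97 | 84.6% | 1.746 | 0.5% | 96.1% |
| 0.2 | 5.88 | 85.6% | 1.720 | 2% | 96.6% |
| 0.3 | 5.72 | 87.4% | 1.674 | 5% | 97.3% |
| 0.5 | 5.20 | 92.8% | 1.520 | 13% | 99.0% |
| 0.7 | 4.28 | 98.6% | 1.253 | 29% | 99.9% |

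The narrowing, 1 − √(1 − r²), is the same at either SD. In sample-size terms the gain is 1/(1 − r²): about 10% more participants at r = 0.3 and 33% more at r = 0.5. If all 122 per group contribute (an upper bound, SD 6.0), power is 93.0% unadjusted and 95.0% at r = 0.3. Spending 8 further degrees of freedom on covariates (SD 6.0, n = 91) changes power by less than 0.001.

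**3. Omitting the strata.** The standard error is inflated by 1/√(1 − share). For shares of 2%, 5% and 10% the ratio is 1.010, 1.026 and 1.054. The actual two-sided alpha of a nominal 5% test becomes 0.048, 0.044 and 0.039.

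**4. Counting the run-in as outcome.** Suppose a constant effect of 2.65 over the 24 reward weeks in Section 6.2, and two run-in weeks with no effect. The averaged difference is 2.65 × 24/26 = 2.45. With SD 6.0 unchanged and 91 per group, power is 78.1%.

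All these are t-test approximations on participant means, not calculations for the weekly mixed model.

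**The case against.** The strongest reply is that nothing is broken. The unadjusted analysis is valid, and the design has slack. The SD was raised by 25%, and 75% retention was assumed although Section 5.3 expects 85%. At 85%, 244 × 0.85/2 is about 103 per group, and unadjusted power is 88.4% at SD 6.0 and 97.6% at SD 4.8. That is correct, and it is why this is a point about precision and not about sample size.

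Second, r is unknown and may be low. The run-in lasts only two weeks and falls inside the novelty period that the protocol expects to fade by about 12 weeks. Screening out dyads who cannot supply run-in data may also narrow its range. This stands: the gains at r = 0.5 to 0.7 have no support in the documents, and r = 0.1 to 0.3 is the more cautious reading. But adjustment costs almost nothing even if r is low.

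Third, a mixed model can carry covariates, and an analysis over time might take the run-in weeks as a baseline time point. Section 12.4 excludes neither, but it states neither. Another prespecified way of using the run-in would be acceptable.

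Fourth, site is loosely defined. The summary allows up to six recruiting sites with visits at three clinic locations, Section 5.3 mentions many more affiliated sites, and Section 5.4.1 glosses site as facility type. That is fair, and the fix has to name the strata as they were coded.

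Finally, the run-in conflict is mostly wording, since every section but 6.2 puts it before randomisation. Counting those weeks as outcome is not the likeliest reading, but nothing in the outcome definition rules it out.

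**Conclusion.** The concern holds. No section names run-in brushing, site or phone type in the primary model, although the first is collected before randomisation and the other two are used in the allocation. The consequence is lost precision. There is no bias, and the 84% power claim is right for the unadjusted test. Under assumed correlations of 0.1 to 0.3 the interval would narrow by 0.5% to 5%, and power at SD 6.0 would rise by 0.4 to 3.2 points. At r = 0.5 the figures would be 13% and 8.6 points. If the pilot SD of 4.8 applies, power is already about 96% and the benefit is mainly a narrower interval. The effect of omitting the strata is probably small. Section 6.2 does conflict with Sections 4, 5.4 and 7.1.2 on when the run-in falls, and the passages need reconciling. The change should be made because it is nearly free, and because covariates chosen after unblinding invite questions about selection.

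**What to change.** In Section 12.4:

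- State the primary model as weekly qualifying episodes on group, time and group × time. Add fixed effects for run-in mean qualifying episodes per week (scaled to the run-in days observed), site and phone operating system, and a random effect for dyad.
- Define site exactly as coded in the randomisation schedule, and say how sparse strata are pooled.
- Name the primary contrast as the group difference averaged over the weeks to the Month 6 visit.
- State that run-in weeks are baseline and are not counted in the outcome.
- Adjust the plaque score for its screening value and the strata. Do not require the binary caries outcomes to be adjusted for their screening status: caries experience is nearly cumulative, so this risks quasi-separation and changes the odds ratio being estimated.
- Keep the unadjusted comparison as a sensitivity analysis.

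In Section 6.2, reconcile the placing of the practice weeks with Sections 4, 5.4 and 7.1.2.

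The cost is a few sentences and the IRB review that Section 15.2 requires for any amendment, completed before arm assignments are unblinded for analysis. No new data and no further participants are needed.

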3.2 Study Outcome Measures

3.2.1 Primary

The primary outcome is toothbrushing performance through the Month 6 visit, measured with a Bluetooth-enabled toothbrush, and expressed as a mean of the number of qualifying half-day toothbrushing episodes per week. A toothbrushing session recorded with the app qualifies to contribute to the weekly count if it lasts at least one minute and occurs within one of the 14 possible half-day windows during a week; only one session per half-day window contributes to the weekly count, which can range from 0 to 14.

A participant qualifies for weekly drawing eligibility as follows:

- Low threshold - if the child's teeth were brushed at least once per day for at least one minute each day of the week;
- High threshold - if the child's teeth were brushed at least once per half-day for at least one minute each day of the week.

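### The only planned missing-data sensitivity analysis (MICE) assumes missing at random, as the primary GLMM does, so it says little about missingness that depends on unobserved brushing and differs by arm

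*Combined protocol and SAP*

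**What the plan says.** Section 12.4 plans intention-to-treat analyses with GLMMs and defends the choice in one sentence: "GLMMs make fewer missing data assumptions than other methods, which assume missing data are missing completely at random". It then names "Multiple imputation using chained equations (MICE) for arbitrary missingness patterns" for sensitivity analyses. It gives no imputation model, auxiliary variables or shift parameter. The protocol and SAP contain no pattern-mixture, tipping-point or reference-based analysis. Missing at random is never named; it is inferred from the methods.

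Section 3.2.1 defines the primary outcome from app data: "A toothbrushing session recorded with the app qualifies to contribute to the weekly count if it lasts at least one minute". The weekly count runs from 0 to 14. No section says whether a week without a sync is scored as zero or as missing.

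Section 6.2 sets the payment rules. For the reward arm, "Failure to sync three times per week will disqualify the participant from receiving any incentives that week for those in an incentive group". For both arms, "All participants, regardless of group assignment, will receive a fixed payment of" $1 per sync, up to three a week, with a reminder before each. Also, "To claim any incentives, including for syncing data, a parent/caregiver and child must attend the follow-up visits".

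**The concern.** A likelihood-based GLMM is valid under missing at random, and so is standard MICE with no shift. A sensitivity analysis is useful when it relaxes the assumption that the main analysis depends on. This one, as described, does not.

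The design gives a specific reason to want that relaxation. A reward-arm family that has already missed the week's brushing threshold has lost its reward-related reason to sync, while a family on course has a strong one. Control families face no such contrast during the first 12 months. Whether a week is observed can therefore depend on the brushing in that week, and do so differently in the two arms. Visit attendance raises a similar question, since the reward arm has more money to collect.

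At stake is the robustness statement for the primary result. The trial could report that multiple imputation confirmed the GLMM when the two share the assumption most open to doubt.

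**Working it through.** Inputs from the documents: difference 2.65, SD 6.0, two-sided alpha 0.05, 91 per group, 84% power, 75% retention over 12 months and 244 dyads (Section 12.2); 85% retention over one year (Section 5.3); weekly count 0 to 14, through Month 6 (Section 3.2.1). Everything else below is an assumption and is marked as such.

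1. **The plan's own figures.** With 91 per group, the noncentral t calculation gives 84.2% power, against the stated 84%. Enrolment is 91 / 0.75 = 121.3, rounded up to 122 per arm, or 244. Both reproduce, and neither depends on this point.

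2. **Do the two methods share a bias?** A small simulation used assumed values: 122 families per arm, 12 weekly values centred on 7 and clipped to 0–14, between-family SD 4.3, within-family SD 2.5, true arm difference zero, 60 runs. The imputation model used arm and the other weeks. Bias is measured against the complete-data contrast.

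| Missingness mechanism (assumed) | Overall missing, reward / control | Bias, mixed model | Bias, MICE |
|---|---|---|---|
| Depends on arm only | 15% / 35% | 0.00 | 0.00 |
| Reward weeks below 7 episodes missing 45% of the time, other reward weeks 5%; control flat 25% | 25% / 25% | +0.29 | +0.30 |

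The Monte Carlo standard error is about 0.01. In the second row both methods are wrong by nearly the same amount, so their agreement would not reveal it. The size depends on the assumed rates.

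3. **Tipping point.** Assume the missing-at-random estimate is 2.65. Let a fraction f of reward-arm families be missing and brush δ episodes/week less than that analysis supposes, with no shift in control. The effect is 2.65 − f × δ. The significance limit is t(0.975, 2n − 2) × SE, with SE = 6.0 × √(2/n). The tipping shift is (2.65 − limit) / f. The SE is held at its observed-data value for simplicity.

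 - 25% missing: 122 × 0.75 = 91.5, taken as 91. SE = 0.889 and limit = 1.755. Tipping shift = (2.65 − 1.755) / 0.25 = 3.58. Shifts of 2, 3 and 4 give effects of 2.15, 1.90 and 1.65; only the last falls below the limit.
 - 15% missing: 122 × 0.85 = 103.7, taken as 103. SE = 0.836 and limit = 1.648. Tipping shift = (2.65 − 1.648) / 0.15 = 6.68.

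 A shift of 2.65 would put the missing reward families at the control mean. The tipping shifts therefore put them 3.58 − 2.65 = 0.93 and 6.68 − 2.65 = 4.03 episodes/week below it.

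4. **Reference-based version.** If missing reward-arm families follow the control distribution throughout, the effect is 2.65 × (1 − f): 2.65 × 0.75 = 1.99 at 25% and 2.65 × 0.85 = 2.25 at 15%. Both stay above their limits of 1.76 and 1.65.

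5. **Direction.** Now assume 15% missing in reward and 25% in control, with missing families in both arms brushing 2 episodes/week less. The true contrast is 2.65 − 0.15 × 2 + 0.25 × 2 = 2.85, so the missing-at-random analysis understates the reward effect by 0.20. If missing families stop altogether, with arm means of 8.15 and 5.5 (5.5 is the pilot mean, assumed here for control), the contrast is 0.85 × 8.15 − 0.75 × 5.5 = 2.80, an understatement of 0.15. In the second simulated mechanism the bias favoured reward.

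**The case against.** The strongest reply is that the design already works against the problem. Both arms earn $1 per sync whatever the brushing, both get reminders, and both receive $30 for attending a visit (Sections 6.2, 7.1.2 and 7.2). Brushing done without the app open is among the transmitted data (Section 4), so a missed sync need not mean a lost week. The run-in removes families who cannot supply data. All this stands and lowers the likely bias. None of it measures what remains.

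Second, 25% is loss over 12 months, while the primary outcome ends at Month 6, and Section 5.5.2 keeps data supplied before withdrawal. If loss were even over the year (an assumption), 12.5% would be gone by Month 6 and about 6% of weeks would be missing. A reference-based effect would then be about 2.65 × 0.94 = 2.48. This also stands, and the figures above are upper illustrations. Early loss would bring them closer: the pilot retained 75% over only 2 months (Section 12.2).

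Third, Section 12.4 leaves the imputation model open. Toothpaste pump weights and questionnaire answers could enter MICE as auxiliary variables, so the two analyses need not agree automatically. That is fair, but the plan does not commit to them, and they would make missing at random more credible without testing departures from it.

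A reader might infer that unequal missingness between arms is enough to bias both analyses. It is not: missingness that depends on arm alone is still missing at random once arm is in the model, and the simulation shows no bias there. A reader might also infer that the bias must flatter the reward. The documents do not settle its direction, and step 5 shows it reversed.

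**Conclusion.** The point holds in a limited form. The plan's single missing-data sensitivity analysis shares the main model's assumption, so their agreement should not be reported as robustness to missingness that depends on unobserved brushing. The reward-arm-only sync condition makes such missingness plausible and potentially different between arms.

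Under the stated assumptions, a result at the design difference would lose significance at a reward-arm shift of about 3.6 episodes/week with 25% missing, or about 6.7 with 15%. These assume that a missing family contributes no weeks at all, which overstates the impact if earlier weeks are kept.

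The documents do not support saying that the primary result would be overturned. Even the reference-based effect at 25% missing, 1.99, stays above the limit of 1.76. Nor do they show how much data will be missing, or whether unsynced weeks will be treated as missing at all. If such weeks are scored as zero, imputation does not apply to them, and that scoring becomes the assumption to examine. This is a cheap improvement to the analysis plan; the GLMM remains a reasonable primary analysis.

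**What to change.** In Section 12.4, before unblinding:

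- Keep the GLMM as the primary analysis.
- State whether a week without a sync is scored as missing or as zero, and report sync completeness by arm.
- Specify the imputation model and make the MICE analysis delta-adjusted, with separate shifts for the two arms, and report the tipping point.
- Add a reference-based version in which missing reward-arm weeks are imputed from the control distribution.

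The cost is SAP wording and modest programming on an imputation already planned. No new data are needed, and sample size and power do not change. The downside is a possibly less favourable robustness statement.
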